## 4.2.2 Protocol Deviations

Protocol deviations will be tracked by the study team throughout the conduct of the study. Data will be reviewed during Blinded Data Review Meeting (BDRM) prior to database lock to ensure all important deviations are captured and categorised.

Protocol deviations that would exclude subjects from PP population may include (but are not limited to) the following:

- Subjects failing to meet inclusion and exclusion criteria but are included in the study
- Subjects without a Day 5 POM VAS assessment
- Subjects with get application compliance <=80% or weight compliance <=65% or weight compliance >=143% or application compliance >=143% with study treatment.
- Subjects taking prohibited medication (Refer Appendix 4)
- Subjects identified with other major protocol deviations

GlaxoSmithKline Consumer Healthcare Confidential

Page 11 of 36

Full details of the major and minor protocol deviations are provided in Appendix 3.

The number and percentage of subjects with any major protocol deviations and with each type of major protocol deviations will be presented by treatment group (PPD ) using ITT population and listed in PPD . Any minor protocol deviations will also be listed similarly PPD .

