6.1 Investigational/Study Product Supplies

The following study products will be supplied by the Clinical Supplies Department, GSK CH:

Table 6-1	Investigational/Study Product Supplies
-----------	--

	Active Treatment ^a	Active Comparator ^b	Placebo Product for Blinding of Active Treatment ^a
Product Name	DDEA 2.32% Gel	DDEA 1.16% Gel	Placebo gel - 0% diclofenac gel
Pack Design	2 x 50 g tubes	4 x 50 g tubes	2 x 50 g tubes
Dispensing Details	1 kit per subject at Visit 1ª	1 kit per subject at Visit 1 ^b	1 kit per subject at Visit 1ª
Product Master Formulation Code (MFC)	CCI	CC	CCI
Dose/Application	Gel – 5 cm (2 g) on 200 cm ²	Gel – 5 cm (2 g) on 200 cm ²	Gel – 5 cm (2 g) on 200 cm ²
Route of Administration	Topical	Topical	Topical
Usage Instructions	Two times daily (BID) (morning and late afternoon)	Four times daily (QID)	Two times daily (BID) (noon and late evening)
Return Requirements	All used/unused samples to be returned	All used/unused samples to be returned	All used/unused samples to be returned
Storage Requirements	Store below 25°C	Store below 25°C	Store below 25°C

^a The study products for the Active Treatment and Placebo Product for Blinding of Active Treatment will be provided in a single kit containing 4 tubes (2 tubes of each study product)

^b The study product for the Active Comparator will be provided in a single kit containing 4 tubes (4 tubes of Active Comparator product)

Table 6-2 Rescue Medication Inform
--

	Rescue Medication
Product Name	500 mg paracetamol tablets
Pack Type	Pack of tablets
Dispensing Details	Dispense at Visit 1. May re-dispense at Visit 3 if necessary.
Product Formulation Code	Commercial product
Dose	One 500 mg tablet with water per dose. May be repeated after 4 hours. Maximum daily dose 2000 mg.
Route of Administration	Oral
Usage Instructions	As needed for pain
Return Requirements	All used/unused samples to be returned
Storage Requirements	Store sealed.

Table 6-3Sundry Items

Sundry Items to be supplied:

Item Name	Supplied By	Pack Type	Dispensing Details	Return/Disposal Details	
				Used Samples	Unused Samples
Urine pregnancy test	GSK/CRO/Site*	Unit	To be used by site staff at visit 1	Dispose at site	Return
Dosing Card	GSK	Each	Included in treatment kit	Return	Return
Subject Diary	CRO	Each	To be provided to subjects	Return	Return

* CRO = Contract Research Organization

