#### 1.3 Treatments

The following treatments will be administered in the study

|   | Active Treatment a                          | Active Comparator b               | Placebo Product for
Blinding of Active
Treatment a |
|---|--|--|---|
| Product Name                                | DDEA 2.32% gel   | DDEA 1.16% gel                               | Placebo gel -0%
diclofenac gel                                   |
| Pack Design                                 | 2 x 50 g tubes   | 4 x 50 g tubes                               | 2 x 50 g tubes  |
| Dispensing Details                          | 1 kit per subject at visit
1ª                       | 1 kit per subject at visit
1 b | 1 kit per subject at visit
1ª                                    |
| Product Master
Formulation Code
(MFC) | CCI  | Commercial Product                           | CCI   |
| Dose/Application                            | Gel – 5 cm (2 g) on 200 $cm^2$                         | Gel – 5 cm (2 g) on 200 cm       | Gel – 5 cm (2 g) on 200 cm                              |
| Route of Administration                     | Topical  | Topical                                      | Topical   |
| Usage Instruction                           | Two times daily (BID)
morning and late
afternoon | Four times daily (QID)                       | Two times daily (BID)
morning and late
afternoon              |

a The study treatments for the Active Treatment and Placebo for blinding of Active Treatment will be provided in a single kit containing 4 tubes (2 tubes each of study treatment)

b The study treatments for the Active Treatment will be provided in a single kit containing 4 tubes

GlaxoSmithKline Consumer Healthcare Confidential

Page 8 of 36

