#### 4.4.1 Study Drug Compliance and Exposure

#### Compliance:

Compliance will be summarized descriptively based on the following points in PPD using ITT and Safety population respetively, PPD by ITT population on the following three :

- 1. % of scheduled applications made
- 2. % of gel used relative to number of actual applications \* 2g, and
- 3. compliance category (Good/Moderate/Poor).
- 1. % of scheduled applications made will be calculated in following way
  - a. % of scheduled applications compliance per tube:
  - Total number of applications made: Compliance will be summerized based on the percent of scheduled application made. Percent of scheduled application made for each dosing time morning, noon, late afternoon and late evening respectively will be calculated in the following manner.
  - If replacement kit number and replacement date (CRF: Study Medication Replacement) are missing -
    - $\circ$  Expected number of application from tube k=(number of applications per day from tube k) \* duration of days in the study ; where, k=1,2,3,4
    - Actual number of application from tube k= (Expected number of application)
       –[sum of (number of missed applications per day from tube k)\* duration of
       days gel is applied i.e. (Day i Day 1)]; where, i=1,2,3,4,5,6,7,8; k=1,2,3,4
    - Percent of scheduled application made from tube k= (Actual number of application from tube k ( where k=1 to 4) / Expected number of application from tube k) \*100.

GlaxoSmithKline Consumer Healthcare Confidential

Page 15 of 36

- If replacement kit number and replacement date (CRF: Study Medication Replacement) are non-missing then
  - Expected number of application from tube k=Sum of [ (number of applications per day from tube k from kit no. x) +(number of applications per day from tube k from kit no. y)\* duration of days in the study]; where x= Old kit # and y= New kit #, k=1,2,3,4
  - Actual number of application from tube k= (Expected number of application from tube k from kit no. x) –[sum of (number of missed applications per day from tube k from kit x)+ sum of (number of missed applications per day from tube k from kit y)]\* duration of days gel is applied i.e. (Day i Day 1)]; where, i=1,2,3,4,5,6,7,8; k=1,2,3,4; x= Old kit # and y= New kit #
- Percent of scheduled application made from tube k= (Actual number of application from tube k ( where k= 1 to 4) / Expected number of application from tube k) \*100% of scheduled applications compliance overall:

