  - Over all Compliance % = [sum of (actual # of application from each tube)/sum of (expected # of application from each tube)\*100]

Scheduled applications will include all scheduled applications through the day before the final visit. On day 1, the percentage of gel used will be calculated based on the possible number of administrations on that day. If only 3 were possible, then 100 % compliance on that day will be considered 3 applications.

- % of gel used relative to number of actual applications \* 2g will be derived as following -
  - Total weight of study medication used: The percent (%) of gel used will be computed relative to the actual number of application made from randomization through the final visit multiplied by 2 g.in two ways –
  - If replacement kit number and replacement date (CRF: Study Medication Replacement) are missing then
  - Expected weight of study medication used from tube k= (number of applications per day from tube k )\*2g \* Expected number of days gel to be applied from tube k
  - Actual weight of study medication used from tube k= [(Baseline weight of tube k (weight of tube k after last day of application ; k=1, 2, 3, 4

GlaxoSmithKline Consumer Healthcare Confidential Page 16 of 36

**Percent of total medication used** = (Actual weight of medication used/Expected weight of medication used)\*100

In case there is repeated usage of single tube in a day then the over usage of the medication will be reflected in weight compliance.

- Compliance category: Compliance category will be defined in the following way -
  - Good: > 80% of the gel has been applied and > 80% of scheduled applications made,
  - Moderate: not Good and not Poor
  - Poor: < 50% of the gel has been applied or < 50% of scheduled applications made.

For subjects applying active gel only twice per day (DDEA 2.32%), an additional compliance computation will be performed relative to the tubes and applications of active gel. If a subject is falls into good compliance category in both (separately for the active gel and also combined with placebo) then that subject will be included in the PP protocol population.

For each subjects time of the first application, application of the study drug each time point each day and the weight of the four tubes on Day 1, 3, 5 and 8 will be listed in **PPD** :

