#### 211206

Statistical Reporting and Analysis plan Draft V2.0 20JAN2021

- 3. Compliance-Sensitivity analysis: Subjects with good compliance has been added in analysis to check if there is any change in variability in POM.
- 4. There will be additional sensitivity analysis conducted for COVID 19 affected subjects for which protocol will not be updated.
- 5. The definition of Per Protocol Population has been modified in the RAP.
- 6. The protocol deviation criterion of compliance has been modified.

Any changes from the originally planned statistical analysis specified in the protocol are outlined in Table 3.

 Table 3
 Changes to Protocol Defined Analysis Plan

| Protocol                                   | Reporting & Analysis Plan    |  |
|--|------------------------------|--|
| Statistical
Analysis
section         | Statistical
Analysis Plan | Rationale for Changes  |
| • Section
12,
Subsection
12.2.6   | • Section 4.4.3              | • Rescue medication can be clearly analysed defining time to event data.   |
| • Section
12,
Subsection
12.2.6   | • Section 4.5.2              | • Sine the "Day 5", 96 hour is not actual 96th hour with respect to first treatment start time, so as per clinical consideration it's start of Day 5 and consider as 0 hour of Day 5.  |
| • New addition                             | • Section 4.5.1              | • Compliance Sensitivity Analysis: This analysis has
been done to check if there is any change in variability
in POM based on good compliance  |
| • New addition                             | • Section 4.7.5              | • COVID analysis: As the pandemic started at the time of recruitment, as per regulatory requirement sensitivity analysis is planned for COVID patients, if any.  |
| • Section
12.2.
Subsection
12.2.1 | • Section 4.2.3              | • It was observed that most of the subjects has $50\% \le$ weight compliance $\le 80\%$ . However these subjects has full and proper Pain on Movement measurements available. Based on these observations it has been decided to re look on the definition of PP Population. |
| • New addition                             | • Section 4.2.2              | • For overdosed subjects the PP exclusion reason was
updated as "Other deviation-weight
compliance >=143% or application   |

GlaxoSmithKline Consumer Healthcare Confidential

Page 28 of 36

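### The SAP's 143% over-use exclusion from the per-protocol set is partly inoperative and can act unequally between the arms

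*SAP*

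**What the plan says.** SAP 4.5.1.2 places the primary analysis on the PP set without imputation. SAP 4.2.2 introduces the PP exclusions as an open list: "Protocol deviations that would exclude subjects from PP population may include (but are not limited to) the following". The compliance item has lower limits (application 80% or less, weight 65% or less) and an upper limit: "weight compliance >=143% or application compliance >=143% with study treatment". SAP section 5, Table 3, gives the purpose of the upper limit in a row beginning "For overdosed subjects the PP exclusion reason was". Neither place says whether the 143% refers to all four tubes or to active gel only.

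SAP 4.4.1 defines the two measures.

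- Applications: "Actual number of application from tube k= (Expected number of application", less the missed applications. The overall figure is "sum of (actual # of application from each tube)/sum of (expected # of application from each tube", as a percentage.
- Weight: actual and expected grams are defined per tube, followed by a percentage of total medication used. The section adds: "In case there is repeated usage of single tube in a day then the over usage of the medication will be reflected in weight compliance".
- For the DDEA 2.32% arm, a further computation uses the active tubes only. A subject who is Good on both the active-only and the combined computation is to be included in PP. Good means more than 80% on both measures, with no ceiling.

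Table 4-1 of the SAP defines PP with the lower limits only (weight above 65%, applications above 80%).

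The documents also disagree on the tube map. The SAP 1.3 table gives the placebo schedule as "Two times daily (BID) morning and late afternoon". Protocol Table 6-1 gives "Two times daily (BID) (noon and late evening"), and SAP Table 1-1 agrees with the protocol.

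**The concern.** The sponsor judged over-use important enough to add an exclusion for it, so the rule should be able to operate and should mean the same thing in both arms. As written, one of its two limits cannot be reached. The other can tolerate more active gel in the DDEA 2.32% arm than in the DDEA 1.16% arm, because two of the four tubes in the DDEA 2.32% arm are placebo.

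What is at stake is who enters the primary analysis set. A PP rule with a different effective threshold in each arm makes the two PP groups less comparable. A rule that does not name its tube set leaves a choice to be made at the data review.

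**Working it through.** **Inputs.** Four applications a day for 7 days (Protocol 6.2) and 2 g per application (Protocol 6.7) give 28 applications and 56 g per subject. In the DDEA 2.32% arm this is 14 active applications (28 g) and 14 placebo applications (28 g). In the DDEA 1.16% arm all 56 g is active. Each DDEA 2.32% subject is supplied with 2 x 50 g = 100 g of active gel (Protocol Table 6-1).

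**The plan's own figures.** The 143% limit has no derivation in the documents to reproduce. The sample size does reproduce: margin 13 mm, true difference 5 mm, SD 22 mm and one-sided 0.025 give 119 per arm for 80% power (stated: about 120), and 120 per arm gives 80.4%. This point does not affect it.

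**Application limit.**

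- Application % = (expected - missed) / expected x 100, with missed at least 0. The maximum is 100%, reached when nothing is missed. Extra applications never enter the numerator.
- With a replacement kit, the formula read literally starts the numerator from the old kit's expected count but puts both kits in the denominator. The result stays below 100% (at most 89% in the cases tried). If total expected applications are used instead, the maximum is again 100%.
- So 143% cannot be reached on either branch. If extra applications were counted, 1.43 x 28 = 40.04, so 41 applications would trigger it. For the 14 active applications, 1.43 x 14 = 20.02, so 21 would.

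**Weight limit, read as total medication.** The active and placebo expected weights are equal in the DDEA 2.32% arm, so pooled % = (active % + placebo %) / 2. The limit is 1.43 x 56 = 80.08 g.

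| Placebo use | Active gel at which exclusion starts | As % of planned active gel |
|---|---|---|
| 100% (28 g) | 80.08 - 28 = 52.08 g | 186% |
| 80% (22.4 g) | 80.08 - 22.4 = 57.68 g | 206% |
| 65% (18.2 g) | 80.08 - 18.2 = 61.88 g | 221% |

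All three amounts are within the 100 g supplied. In the DDEA 1.16% arm the pooled figure is the active figure, so exclusion starts at 143%.

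The reverse also holds. Active 100% with placebo 186% pools to (100 + 186) / 2 = 143%, so a DDEA 2.32% subject with correct active use is excluded.

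**Active-gel check.** A DDEA 2.32% subject with active use of 180% and placebo use of 100% has a pooled weight of 140%, under the limit. If no application is missed, that subject is Good on both computations. Applied to active gel alone, 143% would fall at 1.43 x 28 = 40.04 g.

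**The case against.** The strongest reply is that the rule still works where it matters. The limits are joined by 'or', and SAP 4.4.1 says that over-use is meant to appear in weight. The weight limit operates fully in the DDEA 1.16% arm, for general over-use in either arm, and for active use of 186% or more with placebo at 100%. This stands: the exclusion does not fail as a whole.

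Second, pooling is an inference. An explicit sum over tubes is written only for applications, and SAP 4.4.1 plans an active-gel computation that it links to PP. If the 143% is read as covering that computation too, the inequality between arms disappears. This also stands, but the text does not say so. The link to PP goes through Good, which has no ceiling, so the ambiguity is itself a defect.

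Third, a reader might infer that DDEA 2.32% subjects who over-use active gel necessarily stay in PP. The documents do not establish that. The list is open, it includes other major deviations, and exclusions are settled at the blinded data review. Dosing errors are also captured in the CRF (Protocol 6.2.1).

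Fourth, a reader might infer that the asymmetry can only favour DDEA 2.32%. That is not supported. Placebo over-use can remove correctly dosed DDEA 2.32% subjects, the documents give no dose-response above the planned dose, and blinded tubes give no evident reason to over-use the active pair. Table 3 reports that most subjects had weight compliance between 50% and 80%, so under-use was the common pattern. The primary endpoint is also analysed on the modified intent-to-treat set, which this rule does not touch.

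Finally, a tempting example is a subject who takes one extra active dose and omits one placebo dose each day. Active 150% and placebo 50% pool to 100% by weight. But application compliance is (28 - 7) / 28 = 75%, so the lower limit of 80% already excludes that subject.

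**Conclusion.** The point holds in a limited form. On the SAP's own formula the 143% application limit can never trigger; this needs no assumption. The weight limit is the only working over-use rule, and its tube set is unstated. If it means total medication, the DDEA 2.32% arm reaches it at 186% of planned active gel (placebo at 100%), against 143% in the DDEA 1.16% arm, and placebo over-use alone can also trigger it. The active-gel check supplies no ceiling, and Table 4-1 has no upper limit. Taken literally, the statement that Good on both computations means inclusion in PP also conflicts with the 143% exclusion, and its 80% weight threshold does not match the 65% used elsewhere.

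The documents give no count of affected subjects and no basis for the direction or size of a bias. Purely as an assumption, suppose 2% to 20% of the DDEA 2.32% PP group were retained over-users with 2 to 10 mm of extra relief. The mean difference would then move by 0.02 x 2 = 0.04 mm to 0.20 x 10 = 2.0 mm, against a 13 mm margin. This is a correction that should be made; it does not show that the primary conclusion is unsafe.

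**What to change.** - In SAP 4.4.1, count actual applications from the diary and CRF, including extra ones, so that the percentage can exceed 100%. Protocol 6.8 has every application timed and dated, and Protocol 6.7 has applications recorded per tube.
- In SAP 4.2.2, state that the existing 143% limit applies to the pooled total and also to the morning plus late-afternoon tube pair. Compute the pair for every subject in both arms. No treatment code is then needed, and PP membership can be settled at the blinded review before codes are broken, as Protocol 6.5 and 12.2.2 require. Deriving it after unblinding would conflict with those sections.
- Add the upper limit to Table 4-1, and reconcile the sentence on Good in both computations with the 65%, 80% and 143% limits.
- Reconcile the placebo times in the SAP 1.3 table with SAP Table 1-1 and Protocol Table 6-1, since the pair check relies on the tube map.

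The cost is SAP wording and programming; tube weights and application times are already collected. The downside is small: a few more subjects may leave PP, including some DDEA 1.16% subjects who exceed the limit on the pair but not on the total.

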6.9 Concomitant Medication/Treatment(s)

As a general rule, no concomitant medications should be taken during the study, especially those medications prohibited by the exclusion criteria. Special attention should be given to the prohibited use of systemic or topical NSAIDs from the time of Screening up to Visit 4– as these are the basis for subject exclusion.

Concomitant therapies prohibited during the study:

• Analgesics since the injury, administered by any route (i.e., topical, oral, rectal, injected, or inhaled), except rescue medication as described in Section 6.10, and acetylsalicylic acid taken for at least 30 days on a stable daily dose (≤ 162 mg) for non-analgesic reasons. Pain medication taken prior to the injury must be washed out for at least 24 hours before randomization. The following concomitant medications and/or therapies are prohibited:

- Systemic or topical NSAIDs;
- Steroids (injected or oral, except inhaled topical asthma and hayfever treatments and topical dermal treatments not applied to the sprained ankle);
- Physiotherapy (including, but not exclusive to, transdermal electro neural stimulation (TENS), ultrasound, massage, and spinal manipulation) or any other kind of pain therapy throughout the course of the study;
- Tranquilizers, anxiolytics, hypnotics, or sedatives, unless the subject's prescribed daily dose has been unchanged for a month before the randomization visit; this regimen must continue unchanged for the entire study;
- Amphetamines, barbiturates, benzodiazepines, cocaine, methamphetamines, opiates, phencyclidine, and tetrahydrocannabinol;
- Traditional, herbal or homeopathy treatments (oral and topical);
- Adhesive and/or immobilizing casts, bandages, Aircast splints, treatment by rest, ice, compression, or elevation (RICE) are not allowed.

Subjects will receive paracetamol as rescue medication as described in Section 6.10. Use of a crutch and certain physician approved exercises will be allowed. The physician will instruct the subject to start Achilles' tendon stretching on Day 1.

Any medications, treatments or vaccine (including over-the-counter or prescription medicines, vitamins, and/or herbal supplements) taken during the study, from signing the informed consent, must be recorded in the CRF with indication, reason for use, unit dose, daily dose, and start and stop dates of administration. All subjects will be questioned about concomitant medication/treatments at each site visit.

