12.2.2 Exclusion of Data from Analysis

Exclusion of any data from the analyses will be determined during a Blind Data Review Meeting prior to database lock. Any reasons for exclusion from an analysis population will be listed, if applicable.

Protocol deviations that would exclude subjects from the PP population may include (but are not limited to) the following:

- Subjects failing to meet inclusion and exclusion criteria but were included in the study.
- Subjects without a Day 5 pain on movement VAS assessment
- Subjects with poor or moderate compliance with study treatment
- Subjects taking prohibited medication
- Subjects identified with other major protocol deviations

Further detail is provided in the statistical analysis plan.

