## 1.4 Sample Size Calculation

Approximately 300 subjects will be randomized to ensure at least 240 evaluable subjects complete the study for the Per Protocol (PP) analysis population. A maximum of 40 randomized subjects per center will be considered.

Approximately 120 subjects per treatment arm has been determined to provide 80% power to demonstrate non-inferiority of DDEA 2.32% gel b.i.d with DDEA 1.16% gel q.i.d. by comparing the two-sided 95% CI of the difference in mean change from baseline of VAS POM score between the two products with the non-inferiority margin of 13 mm. This assumes a treatment standard deviation of 22mm and allows for a possible small true treatment difference of 5mm in favor of DDEA 1.16%.

The margin of 13 mm (on a 100 mm VAS scale) was chosen as the literature reported minimally important clinical difference for an acute musculoskeletal injury (Todd et al 1995), with treatment differences smaller than 13mm considered as not clinically important. The standard deviation was obtained from a previous placebo-controlled ankle sprain study VOPO-P-307 with DDEA 2.32% gel.

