#### 4.5.1.2 Statistical Hypothesis, Model, and Method of Analysis

The hypothesis of the study is stated below:

H0: The Diclofenac 2.32% DDEA Gel administered BID is inferior to Diclofenac1.16% DDEA gel administered QID.

 $\mu_T \text{-} \mu_S \geq \delta$ 

Where,  $\mu_S$  is the mean for a standard therapy (Diclofenac 1.16% DDEA Gel administered QID) and  $\mu$ T is the mean for test therapy (Diclofenac 2.32% DDEA Gel administered BID).  $\delta$  is the non-inferiority margin of 13 mm.

H1: Diclofenac 2.32% DDEA Gel administered BID is non-inferior to Diclofenac 1.16% DDEA gel administered QID.

 $\mu_T \text{ - } \mu_s < \delta$ 

 $\delta = 13 \text{mm}$ 

The primary efficacy analysis will be performed on PP population without imputation of missing data. The primary endpoint (Change from baseline in POM ) will be analysed using

GlaxoSmithKline Consumer Healthcare Confidential

Page **19** of **36** 

211206

Statistical Reporting and Analysis plan Draft V2.0 20JAN2021

Analysis of Covariance (ANCOVA) model with treatment and center as factors and baseline POM as covariate.

Diclofenac 2.32% DDEA Gel administered BID will be declared non-inferior to Diclofenac 1.16% DDEA gel administered QID if the upper limit of the two-sided 95% confidence interval of the difference between their mean changes from baseline VAS POM responses is less than the established margin of 13 mm.

Refer sample SAS code in APPENDIX 4.

Assumptions of normality and homogeneity of variances in the ANCOVA model will be evaluated after study un-blinding. If violations are observed then the following will be performed as a post-hoc sensitivity analysis and results will be compared with primary analysis results:

- 1. Suitable data transformations will be tried to achieve the assumptions.
- 2. If suitable transformations cannot be found, then the non-parametric Van Elteren tests will be performed using center as strata. Two sided 95% CI and p value will be presented.

POM by 100 mm VAS analogue scale (CRF page: Pain on Movement ; variable VASSCRL)will be summarized over time (**PPD**) using mITT population. Also POM by 100 mmVAS analogue scale will be summerarized over time by center using mITT population (**PPD**). Above tables (**PPD**) will be repeated for the PP population. POM by 100 mm VAS analogue scale for COVID 19 patients if any will be summarized in **PPD** using mITT population.

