## Appendix 5: Prohibited Medication

The following concomitant medications and/or therapies are prohibited:

- Systemic or topical NSAIDs;
- Steroids (injected or oral, except inhaled topical asthma and hayfever treatments and topical dermal treatments not applied to the sprained ankle);
- Physiotherapy (including, but not exclusive to, transdermal electro neural stimulation (TENS), ultrasound, massage, and spinal manipulation) or any other kind of pain therapy throughout the course of the study;
- Tranquilizers, anxiolytics, hypnotics, or sedatives, unless the subject's prescribed daily dose has been unchanged for a month before the randomization visit; this regimen must continue unchanged for the entire study;
- Amphetamines, barbiturates, benzodiazepines, cocaine, methamphetamines, opiates, phencyclidine, and tetrahydrocannabinol;
- Traditional, herbal or homeopathy treatments (oral and topical);
- Adhesive and/or immobilizing casts, bandages, Aircast splints, treatment by rest, ice, compression, or elevation (RICE) are not allowed.

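### The per-protocol exclusion for prohibited medication has no cut-off at the Day 5 assessment, so a valid primary score can be discarded for something that happened after it was measured

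*SAP*

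**What the plan says.** SAP 4.5.1.2 states: "The primary efficacy analysis will be performed on PP population without imputation of missing" data. Non-inferiority is declared if the upper limit of the two-sided 95% confidence interval for the difference in Day 5 change is below 13 mm.

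The PP exclusions are listed in SAP 4.2.2, including "Subjects taking prohibited medication (Refer Appendix 4"), and in protocol 12.2.2, which has the same item: "Subjects taking prohibited medication". Neither gives a time window. Both lists are introduced permissively, and a blinded data review meeting before database lock settles the exclusions.

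The ban outlasts the primary endpoint. Protocol 6.9 refers to the "prohibited use of systemic or topical NSAIDs from the time of Screening up to Visit 4", and SAP Appendix 5 bars physiotherapy "or any other kind of pain therapy throughout the course of the study". Protocol 4.1 places the primary measurement at Visit 3, 96 ± 4 h after the start of treatment, and Visit 4 at 7 ± 1 days.

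The SAP's cross-reference goes to Appendix 4, which holds sample SAS code. The list of prohibited treatments is Appendix 5.

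**The concern.** A PP exclusion should remove data that a deviation could have distorted. Prohibited use that starts after the Visit 3 assessment cannot distort the Day 5 POM, but a subject who is still in pain at Visit 3 is a plausible candidate to seek other treatment before Visit 4. The criterion, applied as listed, would then select on the outcome through a later event.

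If the 2.32% gel is truly worse, more of its subjects have poor Day 5 scores. More of them would be removed, and the observed difference would shrink. In a non-inferiority trial that is the unsafe direction. Blinding the review meeting to treatment does not prevent this, because the selection works through pain and not through knowledge of the arm.

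The SAP already uses the opposite reasoning elsewhere. Section 5 relaxes the PP compliance rule partly because the affected subjects had complete POM data. Late users of prohibited treatment are in the same position.

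**Working it through.** **Timing.** Nominal treatment lasts 7 × 24 = 168 h. The primary measurement is at 96 h. The ban therefore continues for a nominal 168 − 96 = 72 h after the primary score is fixed. Neither exclusion list, nor the PP definition in SAP 4.2.3, states that use within those 72 h leaves a subject in PP.

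**The plan's own figure.** SAP 1.4 gives "Approximately 120 subjects per treatment arm has been determined to provide 80% power", judged by "comparing the two-sided 95% CI of the difference in mean change from baseline of VAS POM score" "with the non-inferiority margin of 13 mm", with SD 22 mm and a true difference of 5 mm.

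- n per arm = 2 × 22² × (1.960 + 0.842)² / (13 − 5)² = 118.7, so 119 against the stated 120.
- With 120 per arm, SE = 22 × √(2/120) = 2.84 mm and power = Φ(8/2.84 − 1.96) = 80.4%.

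The design reproduces.

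**Illustration of outcome-related removal.** The documents give no rate of prohibited use, so the removal share f is an assumption. The model is:

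1. Day 5 change is normal with SD 22 mm and mean 0 (1.16%) or D (2.32%); higher is worse.
2. One threshold c, common to both arms, is solved so that the average of P(change > c) over the two arms equals f. Everyone above c is removed.
3. Truncated-normal means and variances give the expected PP difference d and its SE, starting from 120 per arm.
4. P(declare non-inferiority) = Φ((13 − d)/SE − 1.96).

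At D = 13 mm, where the correct error rate is 2.5%:

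| f | Removed of 240 | 1.16% arm | 2.32% arm | d (mm) | SE (mm) | False declaration |
|---|---|---|---|---|---|---|
| 0 | 0 | 0 | 0 | 13.00 | 2.84 | 2.5% |
| 0.5% | 1.2 | 0.15% | 0.85% | 12.59 | 2.80 | 3.5% |
| 1% | 2.4 | 0.33% | 1.67% | 12.29 | 2.77 | 4.4% |
| 2% | 4.8 | 0.74% | 3.26% | 11.80 | 2.72 | 6.4% |

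Example, f = 1%: (13 − 12.29)/2.77 − 1.96 = −1.70, and Φ(−1.70) = 4.4%.

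At the planning difference of 5 mm, the expected PP difference falls to 4.82, 4.69 and 4.49 mm for the same shares. At D = 0 it stays 0. Removal unrelated to outcome gives no bias at any D.

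**mITT.** This set requires only randomization and one post-baseline POM. A subject whose prohibited use began after Visit 3 stays in, with an unaltered Day 5 score, so late use does not bias mITT.

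**The case against.** The strongest reply is that the plan does not order this exclusion. The list is permissive, the review meeting decides blind, and PP is tied to major deviations that could confound the efficacy analyses. An event on Day 6 cannot confound a Day 5 score, so the meeting is free to keep the subject. This stands: the fault is a missing timing rule, and a reader who infers that everyone who uses a prohibited treatment is automatically dropped goes beyond the text. It does not remove the need for the rule, because nothing obliges the meeting to keep such subjects. The parenthesis in SAP 4.2.3 about deviations not affecting the primary endpoint is too unclear to rely on.

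Second, other analyses protect the conclusion. Protocol 12.2.5 assesses non-inferiority on PP and mITT, SAP 4.5.1.2 tabulates both, and SAP 4.5.1.3 adds an ITT analysis with imputation. For late use this is a real safeguard: if both PP and mITT had to succeed, the error from this source could not exceed the 2.5% of mITT. But SAP 4.5.1.2 names PP alone as primary and does not state that both must succeed.

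Third, late use may be rare or unrelated to ankle pain. Paracetamol is allowed as rescue, and several items in Appendix 5, such as steroids and sedatives, need not signal poor relief. This also stands, and it is why the size cannot be fixed.

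A reader might also infer that subjects who use prohibited treatment before Visit 3 should be scored as poor responders. The documents do not require that. Removing users of a confounding treatment is an ordinary PP choice, and scoring them otherwise is a debatable choice of estimand and imputation.

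**Conclusion.** The point holds as a gap in the rule. An exclusion with no time limit is attached to an endpoint fixed at Visit 3, so the primary PP analysis can lose a valid Day 5 score because of a later event that the score itself may have prompted.

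The direction is conditional. PP leans towards non-inferiority only if late use follows poor relief and the 2.32% gel is truly worse. The second condition is the case that the test exists to guard against.

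The size is unknown. The figures of about 3.5%, 4.4% and 6.4% assume that all of the worst 0.5%, 1% or 2% of responses are removed under one common threshold, with normal data, SD 22 mm and 120 per arm. They show that one to five subjects from the poor-response tail can matter; they are not estimates. A reader might extend the model to larger shares and infer a serious inflation of error. The documents give no rate to support that, and larger shares would describe prohibited use over the whole study, not the part after Visit 3 at issue here.

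This is a cheap improvement and does not show that the trial's conclusion would be wrong.

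**What to change.** Before unblinding, in SAP 4.2.2 and protocol 12.2.2:

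1. State that, for the Day 5 primary endpoint, this exclusion applies only to prohibited medication or therapy used before the Visit 3 POM assessment. Later use is listed but does not remove the subject.
2. State that later use does not remove the subject through the eligibility bullet either. Exclusion criterion 14 in protocol 5.3 bars analgesics during the study as well as before it, so the first bullet of the same list would otherwise bring the exclusion back.
3. Set a rule for use dated the same day as Visit 3. Protocol 6.9 requires start and stop dates but not times, so the order may be unknown. The rule must be fixed in advance.
4. Correct the reference from Appendix 4 to Appendix 5.

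Report the mITT result beside PP, as protocol 12.2.5 and SAP 4.5.1.2 already provide.

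The cost is a few sentences. Treatment dates and reasons for use are already collected (protocol 6.9), and SAP 4.4.2 already flags forbidden therapies. No new analysis is needed, and PP can only gain subjects. The one drawback is that the PP set for Day 5 may differ from the PP set for the Day 8 secondary endpoints, which late use can affect; the SAP should say so.
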